**A Multicenter Trial of the AIDS Clinical Trials Group (ACTG)**

**DAIDS ES # 11703**

**Clarification Memo Date: 18 April 2013**

---

This clarification memo is being issued primarily to allow the study to open as quickly as possible (ie, before requiring that 4-5 sites are ready to implement the study) (see item #4 below). This change is being made to ensure the feasibility of the current plan for shipment and testing of samples and the near real-time reporting of results (see protocol section 6.3.11). Implementation of this plan at a slightly slower pace than would be expected if 4-5 sites began enrolling at the same time will allow for rapid correction of any issues that arise.

In addition, this memo includes clarifications related to the requirement for rifampin resistance testing (item #1) and to the window for reporting use of certain prescription drugs (item #2), and to remove mention of the FDA in several instances where it is not required (item #3).

The following are the specific clarifications to individual sections of protocol A5290, Version 1.0, 02/17/12:

1. Note A in section 4.2.3 should be understood to read as shown below:

**NOTE A: All specimens available at entry should be tested for RIF resistance. Participants Candidates who meet entry criterion 4.1.3 may be enrolled even if no specimens are available or pending the results of RIF drug susceptibility testing # by a rapid HAIN GenoType MTBDR Plus line probe assay, GeneXpert® MTB/RIF assay, or other rapid MTB RIF drug resistance assay result is not yet available. However, if RIF drug susceptibility test results are not available within 60 days after study entry or if any drug susceptibility testing subsequently demonstrates RIF resistance, participants will be discontinued from the study and referred to their primary clinician/clinical facility or TB and ART program and treated with the best available TB and ART according to local standards of care.**

2. In section 6.3.4, the timeframe for reporting 'Prescription drugs for treatment of opportunistic infections' should be '**Within 30 days prior to study entry**' in the Medication History table (5th row below headers, 2nd column). The current 'Complete history' should be deleted.

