Confirmed extrapulmonary TB is defined as the presence of compatible clinical symptoms as previously described plus clinical features of organs involved, such as sterile pyuria or other renal involvement, pericarditis, ascites, pleural effusion, meningitis, arthritis, orchitis, enteritis, extrathoracic lymphadenitis, or osteitis and positive culture for MTB or nucleic acid amplification test positive for MTB or MTB Complex from fluid or tissue biopsies from any of these organ or tissue sites, including bone marrow, liver, and blood.

Probable Pulmonary TB is based on the clinician's judgment and includes compatible clinical symptoms as previously described, and at least one of the following: 1) positive sputum smear for acid fast bacilli (AFB); or 2) abnormal CXR, chest CT scan or other chest imaging; or 3) evidence of granulomata with organisms positive for AFB or caseating granulomata on lung tissue biopsy; or 4) positive tuberculin skin test (TST) ( $\geq$  5mm) or interferon gamma release assay (IGRA); and without concurrent illness that would explain the findings, but MTB cultures are negative or not available.

Probable Extrapulmonary TB is based on the clinician's judgment and includes compatible clinical symptoms as previously described plus clinical features of organs involved as previously described, or evidence of granulomata with organisms positive for AFB or caseating granulomata on tissue biopsy from relevant site(s); and specific antituberculous therapy initiated or recommended, but MTB cultures are negative or not available.

NOTE: Participants whose qualifying episode of TB was later determined not to be TB will continue to be followed on study but off study drugs for safety and ART endpoints.

- 4.1.4 Chest x-ray within 30 days prior to study entry.
- 4.1.5 A PI-based ART regimen is required, as determined by the participant's primary clinician/clinical facility.

NOTE: Enter the reason, in the eligibility checklist, for the PI-based ART regimen from among the following choices:

The PI-based therapy was required:

- 1) Because the participant failed an NNRTI regimen or;
- 2) Because the participant had an adverse reaction to an NNRTI regimen or;
- 3) Because the participant received single dose nevirapine during pregnancy and could have NNRTI resistance mutations archived at the time the participant was starting ART;
- 4) Other, specify.

4.1.6 Laboratory values obtained within 14 days prior to study entry:

Accrual period 1

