#### 4.2 Exclusion Criteria

- 4.2.1 History of completed TB treatment and resolution of TB symptoms less than 1 year prior to the current TB episode at study entry, or incomplete treatment for a prior episode of TB (i.e., defaulted past TB treatment) at any time prior to the current TB episode.

NOTE: Completed TB treatment is defined as completion of an 8-week intensive phase of TB treatment with INH and RIF plus at least 2 other anti-TB drugs, followed by a 16-week continuation phase of TB treatment with INH and RIF for a total duration of at least 24 weeks of TB treatment.

- 4.2.2 Documented multidrug-resistant tuberculosis (MDR TB) or extensively drug-resistant (XDR) TB.

NOTE: MDR TB is defined as TB with resistance to RIF and INH. XDR TB is defined as MDR TB plus resistance to fluoroquinolones and to at least one second-line injectable anti-TB drug. If MDR TB or XDR TB is determined based on locally-obtained drug susceptibility testing after study entry, the participants will be discontinued from the study and referred to their primary clinician/clinical facility or TB and ART program and treated with the best available TB and ART according to local standards of care.

- 4.2.3 Participants infected with a rifamycin resistant strain of TB as determined by HAIN GenoType MTBDR Plus line probe assay or, GeneXpert® MTB/RIF assay (or, following approval of the core team, a result from another locally-obtained standardized RIF drug susceptibility test). Participants found to have a rifamycin-resistant strain of TB should be referred for management according to the site's standard of care.

NOTE A: Participants may be enrolled pending the results of RIF drug susceptibility testing if a rapid HAIN GenoType MTBDR Plus line probe

assay, GeneXpert® MTB/RIF assay, or other rapid MTB RIF drug resistance assay result is not yet available. However, if RIF drug-susceptibility test results are not available within 60 days after study entry or if any drug susceptibility testing subsequently demonstrates RIF resistance, participants will be discontinued from the study and referred to their primary clinician/clinical facility or TB and ART program and treated with the best available TB and ART according to local standards of care.

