### 6.3.2 Acid Fast Bacilli (AFB), TB Culture, and Drug Sensitivity

At or within 30 days prior to study entry, all participants should have a sputum sample collected for AFB smear, mycobacterial culture, speciation (if culture positive), and TB drug susceptibility (if MTB culture positive) testing to be performed locally or at a reference laboratory. The ability to produce a sputum sample is not a requirement for enrollment into the study; however, once entered, site staff must attempt to obtain a sputum sample and can induce a sputum sample if the participant is not able to produce one on his/her own.

NOTE: If the participant has exclusively extrapulmonary TB and sputum cannot be induced, a sputum sample is not required, but a specimen from any clinically relevant extrapulmonary site (e.g., pleural, pericardial, or peritoneal fluid or tissue biopsy; aspirate of lymph node, cold abscess, bone marrow or joint fluid; cerebrospinal fluid; liver, bone marrow or other tissue biopsy or; blood), if available, should be submitted for AFB smear, mycobacterial culture, and TB drug susceptibility testing.

Documentation for the current episode of TB should include any TB treatment initiated for the qualifying (current) episode prior to randomization, any known TB diagnostic test results available (e.g., culture from any samples, including blood, or cerebrospinal fluid (CSF), drug susceptibility test results, and histopathology results), and any radiologic exams documenting manifestations of TB. Record this information on the CRFs.

At week 8 and week 12, a sputum sample will be collected and tested as above. See below for additional sputum collection instructions if the culture is positive for TB.

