Because the primary objective entails comparing virologic efficacy of Arm A versus Arm B and Arm C versus Arm A, we will have two hypothesis tests and will use an alpha-level of 0.025 for each test (thus, overall alpha-level = 0.05). If we assume the overall virologic efficacy of the double-dose LPV/r arm is 50%, and the standard LPV/r dosed arm coupled with RBT is 70% by 48 weeks (and 80-90% for LPV/r and RAL with RBT-based anti-TB treatment), 147 participants per arm will provide 90% power to detect a 20% difference in virologic response rates by 48 weeks between the double-dose LPV/r arm and the standard LPV/r plus RBT arm and adequate power for the comparison of the standard LPV/r plus RBT arm and adequate power for the comparison of the standard LPV/r plus RBT plus RAL arm compared to both other treatment arms. This assumes using a two-sample, two-sided 0.025-level asymptotically-normal binomial test.

Participants lost to follow-up will be considered as failures. Participants determined to have RIF-resistant TB isolates after enrollment will be taken off study, referred to their local clinician or clinical facility to receive best available local standard of care, and will not be replaced. Assuming that 3% of participants will have RIF resistance at entry and be taken off study, we will need to adjust the sample size to require 152 participants per arm. Adjusting the sample size again by 3% for interim analyses requires 157 participants per arm. Based on these data and assumptions, the estimated overall sample size will be 471 participants.

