#### 9.6.2 Analysis of the Primary Objective

All participants enrolled into A5290 will be included in the analysis of all the overall study objectives regardless of any required dose adjustments for accrual period 1 participants. The protocol team discussed the effect of including participants enrolled during accrual period 1 who underwent dose adjustments in the final analysis of the primary endpoint. The protocol team acknowledges that it is possible that those enrolled during accrual period 1 who had low LPV concentrations and required a dose adjustment might have worse HIV viral load responses at week 48, or alternatively, those who underwent a dose adjustment of one or more study-provided drugs might have greater toxicity that could adversely affect adherence, early treatment discontinuation, and HIV viral load responses at week 48. There remains significant uncertainty around what the major drivers will be of the week 48 virologic outcomes in this setting, such that including all participants in an intent-to-treat analysis accounting for all factors that might have contributed to the endpoint, including low levels requiring dose adjustment, higher toxicity leading to non-adherence or dose interruptions, prolonged intensive TB treatment phase, etc. will be a part of the study analysis plan. The protocol team also acknowledges that it is possible that those enrolled during the accrual period 1 could be different than those enrolled during the accrual period 2. Besides seeking as homogeneous a population as possible, baseline tables of factors that could affect drug concentrations (e.g., sex, prior ART experience, body weight, etc.) will be summarized by accrual period.

The primary outcome variable will be the rates of virologic suppression at 48 weeks within each treatment arm. Participants lost-to-follow-up or without virologic data will be considered failures (i.e., not suppressed). The rate in the double-dose LPV/r arm will be separately compared to the standard dose LPV/r arms in two analyses. The rates between the two arms will be compared using an asymptotic normal binomial test (Arm A versus Arm B; Arm C versus Arm B).

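### Protocol 4.2.3 NOTE A, as printed in Version 1.0, takes anyone without a RIF result by day 60 off study although eligibility admits people who may never have one; whether the clarification memo kept that clause must be checked

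*Protocol*

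**What the plan says.** **The rule.** Protocol section 4.2.3 NOTE A (Version 1.0) lets people enrol while a rapid RIF result is pending. It then says that "if RIF drug-susceptibility test results are not available within 60 days after study entry", or if resistance is later shown, "participants will be discontinued from the study and referred to their primary clinician/clinical facility or TB and ART program". That is removal from the study, not only from study drug.

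**Who is eligible.** Section 4.1.3 accepts probable pulmonary or extrapulmonary TB with supporting findings, "but MTB cultures are negative or not available". Section 6.3.2 adds: "The ability to produce a sputum sample is not a requirement for enrollment into the study".

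**The memo.** Item 1 of the clarification memo of 18 April 2013 opens with "Note A in section 4.2.3 should be understood to read as shown below". Under its wording, candidates meeting 4.1.3 "may be enrolled even if no specimens are available or pending the results of RIF drug susceptibility testing". The 60-day words also appear in the memo text as it reaches the reader.

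**What happens later to participants without culture or smear.** Objective 1.3.1 and section 9.2.3.1 NOTE A give them a week 8 outcome based on clinical and radiographic resolution, then treatment failure from week 24 and relapse by week 72. Section 6.3.7 provides judgment-based outcomes with independent review. Section 8.3 gives six reasons for leaving the study early; it names RIF resistance found after entry but not a missing result.

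**Analysis.** Section 9.6.2 includes everyone enrolled and states: "Participants lost-to-follow-up or without virologic data will be considered failures (i.e., not suppressed". Section 9.4.2 makes one allowance for removal: "Assuming that 3% of participants will have RIF resistance at entry and be taken off study".

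**The concern.** The protocol enrols people for whom a susceptibility result may never exist, defines outcomes for them to week 72, and yet, as printed, removes them at about week 9 because the result is absent. Elsewhere it keeps people under observation. Those later found not to have TB (6.3.5) and TB treatment failures (6.3.2) stay on study, and those who stop all study ARV or TB drugs are encouraged to stay (6.2.7).

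Two things would be at stake if the clause operates. First, week 48 HIV RNA that could have been collected is not, and the participant counts as not suppressed whatever the true viral load. Because the cause is a missing TB specimen, the expected share is the same in every arm, so all suppression rates fall and the contrast shrinks. Second, the TB outcomes after day 60 are lost for these participants.

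**Working it through.** **1. Is the 60-day clause in force?** The memo is a redline printed without its marking. In item 1 two alternative nouns stand side by side at the start of the enrolment sentence, followed later by a stray symbol. In item 4 two different monthly accrual ranges are printed together. The permission to enrol without a specimen is absent from Version 1.0, so it must be new text. The 60-day words occur in both places and could have been kept or struck. The available text cannot settle this.

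**2. Reproduce the plan's sample size.** Inputs from section 9.4.2: 50% (Arm B) versus 70% (Arm A), two-sided alpha 0.025 per comparison, 90% power, normal binomial test. With pooled null variance:

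n = [z(0.9875)·√(2p̄(1−p̄)) + z(0.90)·√(p1(1−p1) + p2(1−p2))]² / (p2−p1)²

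= [2.2414 × 0.6928 + 1.2816 × 0.6782]² / 0.20² = 146.7, so 147 per arm (power 90.1%). Then 147/0.97 = 151.5, so 152; 152/0.97 = 156.7, so 157; 3 × 157 = 471. All match the plan.

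**3. What the 3% allowance implies.** The step from 147 to 152 replaces lost participants, which fits excluding RIF-resistant participants from the analysis. If they are scored as failures, the rates become 0.97 × 50% = 48.5% and 0.97 × 70% = 67.9%, and the same formula gives 159, not 152. So 9.4.2 and 9.6.2 imply different handling of people taken off study.

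**4. Effect of a no-result share q.** The documents give no value for q. Assume 5% to 30%, equal across arms and unrelated to suppression. Let t = 0.03 + q, with 157 enrolled per arm.

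- Scored as failures: p1 = 0.50(1−t), p2 = 0.70(1−t), n = 157.
- Excluded: p1 = 0.50, p2 = 0.70, n = 157(1−t).
- Power = Φ{[(p2−p1)√n − 2.2414·√(2p̄(1−p̄))] / √(p1(1−p1) + p2(1−p2))}.

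Example, q = 10%, scored as failures: rates 43.5% and 60.9%; (0.174 × 12.530 − 2.2414 × 0.7064)/0.6956 = 0.858, so power is 80.5%.

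| q (assumed) | Difference if failures (points) | Power, failures | Power, excluded |
|---|---|---|---|
| 0% | 19.4 | 89.8% | 91.1% |
| 5% | 18.4 | 85.4% | 89.5% |
| 10% | 17.4 | 80.5% | 87.6% |
| 20% | 15.4 | 69.2% | 83.0% |
| 30% | 13.4 | 57.2% | 76.9% |

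**5. Arm C versus Arm B.** Taking 80% for Arm C, the lower end of the plan's range, and removals as failures with the 3% included, power is 97% at q = 20% and 92% at q = 30%. The exposure is mainly in Arm A versus Arm B.

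**6. Type I error.** With equal true rates, multiplying both by the same (1−t) leaves them equal, so the size of the test is not inflated.

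**The case against.** The strongest objection is that the quoted clause may not be the operative text. The memo says how NOTE A is to be read, and its new permission to enrol without a specimen sits more easily with a struck 60-day clause than with a retained one. If it was struck, the memo is itself the alignment, superseded wording is not an error, and the power argument falls away. This stands, and it makes the point conditional.

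Several stronger readings are tempting but not supported:

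- A reader might infer that every participant without a culture is removed. Smear-positive probable TB has a specimen that can be tested, and section 6.3.2 requires sites to attempt sputum, by induction if needed. Only those with no RIF result are affected.
- A reader might infer that none of the TB outcomes for probable TB can be collected. The nominal week 8 visit is day 56, before day 60 (its ±7-day window runs to day 63). It is the later outcomes that are lost.
- A reader might infer that section 8.3 recognises only RIF resistance. It lists other reasons, including investigator judgment; it simply does not name a missing result.
- A reader might take the clause as plainly accidental. The protocol schema and the SAP overview define the population as having RIF-susceptible TB, and the clause can be seen as enforcing that. Dropping it without comment would open another mismatch.

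Scoring removals as failures is also an inference from the general rule in 9.6.2. It is the natural reading, since no exception is stated, but the sample size step in 9.4.2 points to exclusion. Both are therefore shown.

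**Conclusion.** The concern holds conditionally. Version 1.0 NOTE A conflicts with the eligibility of probable TB, with the outcomes defined for participants without culture or smear, and with the omission of a missing result from section 8.3. Whether that conflict survives the memo cannot be read from the available text.

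If the clause stands, the loss of Arm A versus Arm B power depends on a share the documents do not give. At an assumed 10%, power is 80.5% with removals as failures or 87.6% with exclusion, against 89.8% or 91.1% with the planned 3% alone. These figures assume the 50% and 70% design rates, 157 per arm, equal shares across arms, and no link between a missing result and suppression. A reader might infer that the primary comparison is biased towards a false positive. Under these assumptions it is not; the harm is dilution, lost power and discarded data.

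Severity is moderate. SAP section 1.6 states that accrual period 2 will not open, and the SAP covers only the PK and safety interim report, so the 471-participant comparison is not carried out under it. The inconsistency still bears on follow-up of accrual period 1 participants and on any reuse of the design.

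**What to change.** 1. Check the marked copy of the memo. If the 60-day clause was struck, issue a clean NOTE A; nothing more is needed on the conflict itself.
2. If it was kept, reconcile 4.1.3, 4.2.3 NOTE A, the memo, 8.3, 9.4.2 and 9.6.2. State that a missing RIF result does not by itself end study follow-up: these participants are followed through week 72, with week 48 HIV RNA collected and analysed as observed. Bring 1.3.1 and 9.2.3.1 into line.
3. In 9.4.2 and 9.6.2, say whether participants taken off study for RIF resistance count as failures or are excluded, and make the 3% allowance match (159 rather than 152 per arm before the interim allowance if they count as failures).
4. TB and HIV treatment after day 60 for participants without a result, and their fit with the RIF-susceptible population statement, are for the clinical team to reconcile; this point proposes no treatment rule.

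The cost is one clarification and continued visits for the participants concerned. The downside is that some with undetected RIF resistance remain in the TB comparison and slightly dilute it.

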#### 4.3 Study Enrollment Procedures

4.3.1 Prior to implementation of this protocol, and any subsequent full version amendments, each site must have the protocol and the protocol consent forms approved, as appropriate, by their local institutional review board (IRB)/ethics committee (EC) and any other applicable regulatory entity (RE). Upon receiving final approval, sites will submit all required protocol registration documents to the Division of AIDS (DAIDS) Protocol Registration Office (PRO) at the Regulatory Support Center (RSC). The DAIDS PRO will review the submitted protocol registration packet to ensure that all of the required documents have been received.

For studies at non-US sites, protocol activation is required prior to enrolling participants into the study.

Site-specific informed consent forms (ICFs) WILL be reviewed and approved by the DAIDS PRO, and sites will receive an Initial Registration Notification from the DAIDS PRO that indicates successful completion of the protocol registration process. A copy of the Initial Registration Notification should be retained in the site's regulatory files.

Upon receiving final IRB/EC and any other applicable RE approvals for an amendment, sites should implement the amendment immediately. Sites are required to submit an amendment registration packet to the DAIDS PRO at the RSC. The DAIDS PRO will review the submitted protocol registration packet to ensure that all the required documents have been received. Site-specific ICFs WILL NOT be reviewed and approved by the DAIDS PRO, and sites will receive an Amendment Registration Notification when the DAIDS PRO receives a complete registration packet. A copy of the Amendment Registration Notification should be retained in the site's regulatory files.

For additional information on the protocol registration process and specific documents required for initial and amendment registrations, refer to the current version of the DAIDS Protocol Registration Manual.

Once a candidate for study entry has been identified, details will be carefully discussed with the participant. The participant will be asked to read and sign the approved protocol consent form. For participants from whom a signed informed consent has been obtained, an ACTG Screening Checklist must be entered through the Data Management Center (DMC) Subject Enrollment System.

